6.2. Surgical Technique

The medical device will be implanted using standard surgical technique, depending on the investigator's standard procedure. Instrumentation specific for the device will be used. A surgical technique brochure for implanting the acetabular cup and femoral modular heads/sleeves will be provided to each investigator. Separate surgical technique brochures are available that are specific for the stem that will be used with the modular heads.

Soft tissues should be repaired after surgery in order to minimize the risk of limping and dislocation.

Surgery performed by residents and by utilizing Computer Assisted

Orthopaedic Surgery (CAOS) or minimal invasive surgery (MIS) technique will be allowed. Use CAOS or MIS and surgery performed by residents will be documented in CRFs for further analysis.

There will not be any standard protocol for antibiotic or thrombo-embolic prophylaxis. However, all sites are encouraged to follow-up the same prophylaxis protocol during the enrolment period.

Smith & Nephew - Confidential/Study ProtocolR3H01/01Feb2017/Version2.0/BNA including PAS

7. Treatment and Follow-up Evaluations

7.1. Schedule of Events

The intervals and schedule of events is provided in Table 1.

Study Activity	Preop	Ор	DC	3M (+14d)	1Y (+2m)	3Y (+3m)	5Y (+6m)	7Y (+6m)	10Y (+6m)
Inclusion/Exclusion	Х								
Informed Consent	Х								
Demographics/Med History	Х								
Harris Hip Score	Х			Х	Х	Х	Х	Х	Х
UCLA	Х			Х	Х	Х	Х	Х	Х
HOOS	Х			Х	Х	Х	Х	Χ	Х
Radiograph Evaluation			X		X*	×	X	X	X
Operative		Х							
Discharge			Х						
Adverse Events		Х	Х	Х	Х	Х	Х	Х	Х

^{*} Full pelvic overview

7.2. Preoperative Evaluation

Information will be collected on the study population prior to device implantation. Demographic factors including age, gender and primary diagnosis will be obtained. Preoperative clinical status will be determined through a clinical evaluation. The Harris Hip Score¹⁶, the HOOS questionnaire¹⁵ and the UCLA Rating¹⁷ will be collected for all patients.

7.3. Operative-Discharge Evaluation

Information on the operative procedure for each subject including surgical approach, component size, surgical time, and intraoperative blood loss and patients' American Society of Anesthesiologists (ASA) score¹⁹ will be obtained. Additionally length of hospital stay and discharge to home or any other institution will be recorded. Any operative complications, both during the operation and prior to discharge will be collected. Any complication device-related, surgery related or otherwise will be collected.

Patients will have radiographs taken after implantation (before discharge) from the hospital to establish a baseline. Postoperative patient mobilization is will be conducted according to the clinic's standard protocol.

7.4. Postoperative Follow-up Evaluations

Subjects will be seen at the 3 months, 1 year, 3 years, 5 years, 7 years and 10 years interval post surgery. The Harris Hip Score will be collected and the HOOS and UCLA questionnaire obtained at each visit.

Anteroposterior (AP) and (shoot trough) lateral radiographs of the operated hip will be taken before discharge in addition to at 1 year, 3 years, 5 years, 7 years and 10 years postoperatively. At least the 1 year follow-up radiograph should include full pelvic overview (including at least 20 cm of the proximal femur). Pelvic AP radiograph will be used for analysis of cup inclination and leg length discrepancy.

Postoperative radiographs will be taken to determine component alignment, radiolucencies^{20,21}, and bone condition. The alignment of the femoral prosthesis will be measured as the angle between the central axes of the proximal femoral canal and the femoral prosthesis. Angles will be classified as varus, valgus or neutral²². The angle of the acetabular cup will be

Smith & Nephew - Confidential/Study ProtocolR3H01/01Feb2017/Version2.0/BNA including PAS

assessed by measuring the angle of vertical tilt of the acetabular cup (angle between a line joining the ischial tuberosities and one through the long axis of the ellipse of the acetabular cup)²³. Additionally, the cup anteversion will be recorded. Observations will be recorded on the x-ray case report form and independently reviewed.

7.5. Telephone Follow-Up

If subjects are unable to return for follow-up visits to the investigator's office, they may be contacted by telephone to assess their status. Subjects will be asked whether the study device is in place or has been revised, and patient satisfaction will be assessed. This information will be recorded on the corresponding CRF.

8. SAFETY REPORTING

An adverse event assessment will be conducted at each follow-up interval. Data from each visit will be recorded on the study CRFs. All adverse events, regardless of their relationship to the study device, occurring from the time of study device implantation through to study completion should be recorded on the appropriate CRFs and reported as below.

8.1. Definitions for safety reporting

A. Adverse Event (AE)

An AE is any untoward medical occurrence, unintended disease or injury, or untoward clinical signs (including abnormal laboratory findings) in subjects, users or other persons, whether or not related to the study medical device.

B. Serious Adverse Event (SAE)

A SAE is any adverse event that:

- resulted to death,
- was life threatening (at the time of the event); or
- resulted in hospitalization (initial or prolonged); or
- resulted in a disability or permanent damage (a significant, persistent or permanent change, impairment, damage or disruption in the patient's body function/structure, physical activities and/or quality of life);or
- resulted in a congenital anomaly or birth defect; or
- required medical or surgical intervention to preclude permanent impairment of a body function or prevent permanent damage to a body structure; or
- does not fit the other outcomes above, but may jeopardize the subject and may require medical or surgical intervention (treatment) to prevent one of the other outcomes.

Planned hospitalization for a pre-existing condition, or a procedure required by the protocol, without serious deterioration in health, is not considered a serious adverse event.

C. Unanticipated Serious Adverse Device Effect (USADE)

Any serious adverse effect on health or safety or any life-threatening problem or death caused by, or associated with, a device, if that effect, problem, or death was not previously identified in nature, severity, or degree of incidence in the investigational plan or application (including a supplementary plan or application), or any other unanticipated serious problem associated with the device that relates to the rights, safety, or welfare of subjects.

The Investigator will assess and categorize AEs as mild, moderate or severe based on the following definitions:

- Mild: the subject is aware of the sign or symptom, but finds it easily tolerated. The event is of little concern to the subject and/or little clinical significance. The event is not expected to have any effect on the subject's overall health or wellbeing.
- Moderate: the subject has discomfort enough to cause interference with or change in usual activities. The event is of some concern to the subject's health or wellbeing and may require medical intervention and/or close follow-up.
- Severe: the adverse event interferes considerably with the subject's usual activities. The event is of definite Smith & Nephew Confidential/Study ProtocolR3H01/01Feb2017/Version2.0/BNA including PAS

concern to the subject and/or poses substantial risk to the subject's health or well-being. The event is likely to require medical intervention and/or close follow-up and may be incapacitating or life threatening. Hospitalization and treatment may be required.

The Investigator is responsible for assessing the relationship of the AE to the study device and study procedure based on the following definitions:

- Unrelated: the event is clearly not related to the study device or study procedure
- Possible: the event may or may not be related to the study device or study procedure. A relationship cannot be ruled out.
- Probable: the event is likely related to the study device or study procedure. A relationship cannot be ruled out.
- Definite: the event is clearly related to the study device or study procedure.

D. Reoperation and Revisions

A reoperation is any surgical procedure of the study hip. A revision is a surgical procedure of the study hip where one or more of the study components are removed and replaced with new implants.

All reoperations and study component revisions should be documented on the Adverse Event CRF.

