The R3 system offers four XLPE liner options – 0 degree, 20 degree, 0 degree +4 and 20 degree +4. Conventional polyethylene will not be offered. The Smith & Nephew 10 Mrad, fully annealed XLPE is the only cross-linked polyethylene proven to produce less volume of wear debris particles in all head size ranges. Less wear debris provides a chance for reduced osteolysis.

Metal-on-metal

Early experience with metal-on-metal (MoM) bearings validated the concept of this articulation surface for THA⁹. In particular, the wear properties of MoM bearings received greater attention as the limitations of MoP bearings became known. Although the long-term success of the McKee-Farrar and Ring THA systems is attributed in part to a high carbon cobalt chrome molybdenum (CoCrMo) alloy used to produce the devices in the 'as cast' metal, reasons for failures of these devices include the limitations of manufacturing methods at the time these devices were produced¹⁰. The newer MoM prostheses utilize improved bearing geometry and new surface finishings that promote lubrication. Mid-term follow-up on these prostheses demonstrates equivalent safety and effectiveness outcome compared to MoP prostheses¹¹. They offer the potential for greatly reduced wear. Metal bearings are available in several sizes. Large femoral heads can provide increased range of motion and greater stability, which can significantly reduce the risk of hip dislocation¹².

Superior metallurgy and optimal clearances, also used in the clinically proven, highly successful, world-leading BIRMINGHAM HIP Resurfacing System (BHR), provide the R3 Metal-on-Metal system superior performance. The R3 Metal-on-Metal and the

BHR system utilize high-carbide cobalt chrome in the as-cast micro-structural condition, providing superior wear resistance. The R3 provides specific metal inserts for large femoral head sizes (Ø38mm – 54mm heads in shell sizes 50mm – 68mm) which are either combined with the modular BHR heads or the BHR resurfacing.

3. Study Objective

The objective of this study is to determine the long-term safety and effectiveness of the R3 Acetabular System

Hypothesis: implant survivorship (Kaplan-Meier) (revision for any reason) of the R3 cup is at least 97% at 3 years, 95% at 5 years, 93% at 7 years, and 90% at 10 years follow-up.

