8.3. Explantations

In the short term, explantations will usually occur due to acute/chronic infection, instability, and/or subject experiencing severe pain due to various causes. Reduced mobility alone, if it occurs, is typically not a predominant factor in prompting revision surgery. Long-term, aseptic loosening and/or severe pain may become a determining factor as to whether to proceed with device revision. Reasons for removal are not limited to these circumstances alone. The Sponsor requests Investigators to return any revised R3 Hip System components for retrieval analysis.

Explanted components are sterilized by steam autoclave or other appropriate sterilization method according to the Institution's standard sterilization procedures. Only properly packaged explants should be shipped, and the Sponsor notified before any shipment. If possible, the Sponsor will collect histological (bony ingrowth quality, bone quality, response to potential wear debris, etc.) and metallurgical (metal wear, deformation, cracking, corrosion, etc.) information from explants. For all explants, the investigator must record and forward a description of intra-operative findings including: 1) presence of

wear debris, 2) what types of hip components are being replaced, 3) and intraoperative findings relating to the device failure. Explant analysis will occur through the duration of this study.

It should be noted that the Sponsor is not always able to retrieve known explants. Some surgeons may refuse to return explants, and some institutions/hospitals will not release explanted component(s) due to their "policies."

9. Statistical Methods

Evaluations after database closure will be performed on an Intention to Treat (ITT) basis. The analysis will include the descriptive statistics of patient demographics and baseline characteristics. Accountability data will include the number of patients enrolled and the follow-up data collected. Data will be analyzed for changes from preoperative at 3 months, 1 year, 3 years, 5 years, 7 years and 10 years. Safety will be assessed by identifying and summarizing device-related adverse events throughout the study. Analysis of the success rate will be performed using Kaplan-Meier (KM) Survival Analysis. The KM estimate of the success rate along with the 95% confidence interval of the estimate will be included in the final report.

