4.4 Handling of missing and incomplete data

The number of patients with missing data will be presented under the "Missing" category, if present.

When continuous data are being summarized, only the non-missing values will be evaluated for computing summary statistics.

A sensitivity analysis will be carried out comparing results of the original analysis to the results of an analysis where all missing data are assumed to be failures.

A second sensitivity analysis will be carried out using multiple imputation of the missing data in the form of a tipping point analysis. Multiple scenarios will be analyzed, each with a different number of missing data points imputed as successes for each treatment group. (Missing data points not imputed as successes will be imputed as failures.) The purpose of the analysis is to find the tipping point where a certain number of success imputations for each treatment group causes the inference to reverse.

In general, partial dates will be imputed as follows:

- if only the day is missing, the first day of the month will be assumed;
- if the day and the month are missing, January 1st will be assumed;
- if a date is completely missing or unknown the patient's data will not be included for analysis

Protocol Number: TBD Version 0.3

Forms							
Title	Title Statistical Analysis Plan Template						
Co	Code Version Effective Date Page						
FRM_S	FRM_ST03_032 0.3 23 Apr 2015 9 of 12						

5. Evaluation of Demographic and Baseline Characteristics

Given the nature of this study, the demographic data have been already obtained. The demographic and baseline characteristics will be summarized using descriptive statistics for the Enrolled Set.

6. Patient Accounting

Patient accounting will be presented according to the recommendations in the FDA guidance entitled "Clinical Data Presentations for Orthopedic Device Applications".

- Actual A: Subjects with complete data for the primary endpoint, evaluated per protocol, in the window time frame.
- Actual B: Subjects with any follow-up data reviewed or evaluated by investigator ("all evaluated" accounting).
- Theoretical: Number of subjects that would have reached the beginning of the study window associated with each visit if all subjects returned.
- Deaths: Cumulative number of subjects that died during or prior to the study visit.
- Failures: Cumulative number of subjects that failed (revision) during or prior to the study visit.

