7.1 Analysis of primary endpoint

The primary endpoint is implant survivorship at 10 years post study procedure.

Since this Post-Approval Study (PAS) is intended to document the long-term survivorship of the DOD treatment group only and no comparison to a control is required, no formal statistical hypothesis testing will be conducted.

Implant survivorship will be measured from time of surgery to time of the first instance of removal of any device component for any reason. Subjects who do not experience a removal for any reason will be censored at the date of last data collection.

Protocol Number: TBD Version 0.3

Forms					
Title Statistical Analysis Plan Template					
Code		Version	Effective Date	Page	
FRM_ST03_032		0.3	23 Apr 2015	10 of 12	

Kaplan-Meier (KM) estimates will be provided by time point (life tables) and graphically (survival curves).

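### Revision is defined as removal plus replacement, so an explant without reimplantation, read literally, is no event under the main hypothesis or in SAP Failures, but is one in the PAS Kaplan-Meier

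*Combined protocol and SAP*

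**What the plan says.** **Definition.** Protocol 8.1.D defines a revision as surgery on the study hip in which "one or more of the study components are removed and replaced with new implants". PAS addendum 8.1.D and SAP 8.5 repeat it. No other definition of revision appears.

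**Main study.** The hypothesis in protocol Section 3 is that "implant survivorship (Kaplan-Meier) (revision for any reason) of the R3 cup is at least 97% at 3 years", followed by 95%, 93% and 90% at 5, 7 and 10 years. Protocol Section 9 says only that "Analysis of the success rate will be performed using Kaplan-Meier (KM) Survival Analysis"; it defines neither the event nor the censoring.

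**PAS.** SAP 7.1, like addendum 9.1, says: "Implant survivorship will be measured from time of surgery to time of the first instance of removal of any device component for any reason". Replacement is not required.

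**Accounting.** SAP Section 6 returns to revision: "Failures: Cumulative number of subjects that failed (revision) during or prior to the study visit". Expected is Theoretical less deaths and revisions, and it is the denominator of the follow-up rate.

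**The concern.** The definition sets two conditions, removal and replacement. A component taken out and not replaced meets only the first. The case is foreseeable: protocol 8.3 is about explantations and lists infection first among the short-term causes.

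Two things are at stake. In the main study, a definition that leaves out some removals can only raise survivorship, and that figure is set against 97/95/93/90%. In the PAS, the SAP would disagree with itself, because the same subject would be an event in the Kaplan-Meier but not a failure in the accounting table. If the rule is left open, someone must decide how to classify these cases after seeing them.

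**Working it through.** **Inputs**
- PAS cohort: 137 subjects, with one death and one revision by 3 years, leaving 135 (addendum 3 and 9.2; SAP 3.1 and 3.3).
- Stated 3-year Kaplan-Meier: 99.3%, 95% CI 97.4% to 100.0% (SAP 3.5.1).
- Main study: 500 patients (protocol 3.2); thresholds from protocol Section 3.
- Not in the documents: k, the number of explants without reimplantation. I assume k = 0 to 5 and ignore censoring unless stated.

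**Step 1: the plan's own figure.** One event in 137 gives S = 136/137 = 0.9927, or 99.3%, which matches. The Greenwood standard error is √(0.9927 × 0.0073 / 137) = 0.0073, so a plain 95% lower limit is 0.9927 − 1.96 × 0.0073 = 97.8%, against the printed 97.4%. Numbers at risk are not given, so I draw nothing from that difference, and the point does not depend on it.

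**Step 2: the rules side by side**

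| Place | Event named | Explant without reimplantation, read literally |
|---|---|---|
| Protocol 3 | revision | not an event |
| Protocol 9 | none defined | undetermined |
| Addendum 9.1, SAP 7.1 | removal | event |
| SAP 6 Failures | revision | not counted |
| SAP 6 Expected | subtracts deaths and revisions | stays in |

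**Step 3: PAS.** Beyond the one known revision, k such cases give a removal-based Kaplan-Meier of 1 − (1 + k)/137. For k = 1 to 5 this is 98.5, 97.8, 97.1, 96.4 and 95.6%. SAP 7.1 already produces these values. The Failures row would still show one failure, which corresponds to 99.3%. The gap is 1/137 = 0.73 points per case. For a later explant with an assumed 120 or 80 still at risk, one case is worth (136/137)/120 = 0.83 or (136/137)/80 = 1.24 points. Expected would stay at 137 − 1 − 1 = 135 instead of 135 − k.

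**Step 4: main study.** The gap is 1/500 = 0.20 points per case. The thresholds allow 500 × 0.03 = 15, 500 × 0.05 = 25, 500 × 0.07 = 35 and 500 × 0.10 = 50 failures. As an illustration placed deliberately at the 10-year threshold, take 50 replaced components plus k unreplaced explants. Under revision the result is 1 − 50/500 = 90.0% for every k. Under removal it is 1 − (50 + k)/500, which falls from 89.8% at k = 1 to 89.0% at k = 5. Nothing in the documents suggests that the study will end there.

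**The case against.** The strongest reply is that no text says an explant counts as a surviving implant. The definition stands among the safety-reporting definitions, and the hypothesis does not refer to it. Protocol Section 9 leaves the event undefined. Other text points towards counting removals:
- Telephone follow-up (protocol 7.5) treats revised as the opposite of still in place.
- Protocol 8.3 uses explantation, removal and revision loosely and asks for findings on device failure for every explant.
- The telephone form asks about removal.
- The Adverse Event form has one date field for removal or revision.

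This stands as far as it goes: a sensible analyst might count removals anyway. It does not remove the inconsistency, because the only written definition says otherwise and SAP 8.5 repeats it in the plan whose Failures row depends on the word.

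Three stronger readings are tempting but not supported:
- *The PAS survivorship result is inflated.* It is not; SAP 7.1 and addendum 9.1 count every removal.
- *In a staged exchange the event date moves to the second operation, or a subject lost between stages is censored as a survivor.* The documents never mention staged exchange and set no such dating rule. The Adverse Event form can hold the removal date, and for deaths it asks whether the prosthesis was in situ.
- *The definition will carry the main study over a threshold.* That needs counts the documents do not give. The main protocol also sets no test or decision rule for the thresholds; it reports the estimate with a 95% confidence interval.

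**Conclusion.** The inconsistency is real and should be corrected. Applied literally, the shared definition leaves unreplaced explants out of the main hypothesis and SAP Failures and keeps them in Expected, while the PAS Kaplan-Meier counts them. For the main study this is the literal consequence of the wording, not a stated rule, because protocol Section 9 names no event. Within the SAP, the conflict between Sections 6 and 7.1 lies in the text itself.

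The size is 0.2 points per case in 500 for the main study. In the PAS it is one missing failure per case in the accounting table, worth 0.73 points in 137. Both figures ignore censoring, and the number of cases is unknown. The one event reported so far is described as a revision and agrees with the stated 99.3%, so it shows no discrepancy to date. The effect is probably small unless a result falls close to a threshold; in the main study its direction can only be favourable.

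**What to change.** For endpoint and accounting purposes, adopt one failure event: the first removal of any component for any cause, with or without replacement, dated at that removal.
- Use it in the protocol Section 3 hypothesis, in the protocol Section 9 Kaplan-Meier and in SAP 6 Failures and Expected.
- Align the revision definitions in protocol 8.1.D, addendum 8.1.D and SAP 8.5 with SAP 7.1.
- State whether the main hypothesis, which concerns "implant survivorship (Kaplan-Meier) (revision for any reason) of the R3 cup", counts removal of any component or only of cup components. A common event does not settle how head-only or stem-only removals are treated.
- Reconcile the wording on revised or exchanged components in addendum 7.2 with the chosen event.
- Specify that the shared date field on the Adverse Event form holds the date of first removal.

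No new data item is needed. The cost is a protocol and SAP amendment, with FDA and ethics committee approval first if it is judged to affect scientific soundness (protocol 16, addendum 10.2). Events already classified must be rechecked, and main survivorship may come out slightly less favourable.
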